2.3 Primary Endpoint Analysis

The purpose of the primary endpoint is to evaluate the rate of TLF of the Orsiro stent at 1 year compared to a performance goal of 6.9%.

 $H_{0}:$ The TLF rate of the Orsiro stent at 1 year is greater than or equal to a performance goal of 6.9%

Rate ≥ 6.9%

 $H_a:$ The TLF rate of the Orsiro stent at 1 year is less than a performance goal of 6.9%

Rate < 6.9%

Version 1.0 05-18-2022

Confidential

Page 4 of 11

Do not copy or distribute without sponsor approval

A rejection of the null hypothesis (H_{\circ}) would demonstrate that the primary endpoint is met.

TLF is defined as a composite of cardiac death, target vessel-MI or clinically-driven TLR. Target vessel MI will utilize the SCAI definition² for peri-procedural MI and the BIOFLOW-V protocol definition³ for spontaneous MI.

The primary analysis of the primary endpoint of the TLF rate of the Orsiro stent at 1 year will be in the intent-totreat (ITT) population. The primary endpoint will be tested against a performance goal of 6.9% using a one-sided, exact test for one proportion with a Type I error level of 0.025. An additional (one-sided) supporting analysis will be performed in the PP population. A Kaplan-Meier survival analysis (time-to-event) for the primary endpoint outcome will be performed for the ITT and PP populations.

For each analysis population, subjects who have sufficient follow-up data (at least 330 days of follow-up), based on all available collected dates, or experienced the primary endpoint will be included in the primary endpoint analysis.

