3.4.4 Lost to Follow-up

Subjects lost to follow-up are those for whom contact is lost despite the investigator's best efforts to locate the subject. Study sites should attempt to contact these subjects in order to maintain study visit compliance and all contact attempts should be documented. At a minimum, the site should make two attempts to contact the subject by phone and one attempt by certified mail and document the contact attempts.

In the event the subject cannot be contacted using the above methods, the subject is terminated from the clinical investigation by completing a Study Termination eCRF. Subjects are not eligible to be exited as lost to follow-up until after the 1-Year Follow-up. If the 1-Year Follow-up was not completed and subject could not be contacted, and the required contact attempts (at a minimum) have been documented, then lost to follow-up may be an acceptable reason for exit.

The date of exit in the Study Termination eCRF is the date that the site determines the subject to be lost to follow-up. The date of last documented contact with the subject will also be collected. Both dates should be clearly documented.

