4.3.3 Analysis Methods

All clinical data will be analyzed based upon the pre-defined analysis populations. The following methods will be used to evaluate the study endpoints.

Primary Endpoint

The primary analysis of the primary endpoint of the TLF rate of the Orsiro stent at 1 year will be in the intent-to-treat (ITT) population. The primary endpoint will be tested against a performance goal of 6.9% using a one-sided, exact test for one proportion with a Type I error level of 0.025. A supporting analysis will be performed in the PP population. A Kaplan-Meier survival analysis (time-to-event) for the primary endpoint outcome will also be performed in the PP population.

For each analysis population, subjects who have sufficient follow-up data (at least 330 days of follow-up) or experienced the primary endpoint will be included in the primary endpoint analysis.

Secondary Endpoints

There are no formal hypotheses for the secondary endpoints. Secondary clinical endpoints 1 through 7 will be evaluated prior to discharge, at 1 month, 1 year, and annually thereafter through 5 years of follow-up. Analyses of these secondary endpoints will be carried out on the ITT and PP analysis populations:

1. All-cause death.
2. MI.
3. Cardiac death or MI.
4. MACE and individual MACE components (MACE: composite of all-cause death, Q-wave or non-Q-wave MI, and clinically-driven TLR).
5. TLF (evaluated at 2, 3, 4, and 5 years) and individual TLF components (TLF: composite of cardiac death, target vessel Q-wave or non-Q-wave MI, and clinically-driven TLR).
6. TVF and individual TVF components (TVF: composite of cardiac death, target vessel Q-wave or non-Q-wave MI, and clinically-driven TVR).
7. Stent thrombosis (definite, definite/probable, probable) according to Academic Research Consortium (ARC)-2¹ criteria for acute, subacute, late, very late and cumulative stent thrombosis.

Analyses of the following additional secondary endpoints will be carried out on the ITT and PP analysis populations.

1. Device success
2. Lesion success
3. Procedure success

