2.6 Analysis of Secondary Endpoints

There are no formal hypotheses for the secondary endpoints. The secondary endpoints in the BIOFLOW-VII study will be analyzed using frequentist methods when the time points defined below have been met. For each endpoint, the proportion and denominator will be calculated and reported. Analyses of secondary endpoints will be carried out on the ITT and PP analysis sets when data is available for all subjects at the time point. However, there will be no direct imputation of missing data.

The following secondary clinical endpoints will be evaluated prior to discharge, at 1 month, 1 year and annually thereafter through 5 years of follow-up (refer to Sec. 1.4 for definitions):

- 1) All-cause death
- 2) Protocol-defined MI
- 3) Cardiac death or protocol-defined MI
- 4) MACE and individual MACE components
- 5) TLF and individual TLF components (1-year TLF rate is the primary endpoint)
- 6) TVF and individual TVF components
- 7) Stent thrombosis according to ARC-2 criteria¹

Included in the analysis will be subjects experiencing the event or who have adequate follow-up (e.g., at least 23 days for 1-month time point and at least 330 days for the 1-year time point, 660 days for the 2-year time point, 1020 days for the 3-year time-point, 1380 days for the 4-year time point, and 1740 days for the 5-year time point.)

The following secondary endpoints will also be evaluated (refer to Sec. 1.4 for definitions):

- 8) Device success
- 9) Lesion success

Version 1.0 05-18-2022

Confidential

Page 6 of 11

Do not copy or distribute without sponsor approval

10) Procedure success.

Analysis of secondary endpoints 1-7 will be based on CEC adjudicated event data. Analysis of secondary endpoints 8-10 will be based on site-reported data (with CEC adjudicated event data for endpoint 10, as applicable). In evaluating procedure success, MACE will be based on CEC adjudicated event data.

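### The event-or-threshold inclusion rule leaves the end of follow-up undefined at year 1, and gives distorted crude rates at years 2-5

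*SAP*

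**What the plan says.** SAP 2.3 tests the crude 1-year TLF proportion against 6.9% and includes "subjects who have sufficient follow-up data (at least 330 days of follow-up), based on all available collected dates, or experienced the primary endpoint". Protocol 4.3.3 has the rule without the phrase about dates: "subjects who have sufficient follow-up data (at least 330 days of follow-up) or experienced the primary endpoint". SAP 2.6 repeats it for the secondary endpoints: "Included in the analysis will be subjects experiencing the event or who have adequate follow-up". The thresholds there are 330 days at year 1, then "660 days for the 2-year time point, 1020 days for the 3-year time-point", then 1380 and 1740 days. The output is a proportion with its denominator, and on missing data SAP 2.6 says: "However, there will be no direct imputation of missing data".

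Protocol 3.4.4 records two dates for a lost subject. One is the exit date: "The date of exit in the Study Termination eCRF is the date that the site determines the subject to be lost to follow-up". The other is the last contact: "The date of last documented contact with the subject will also be collected". It also states: "Subjects are not eligible to be exited as lost to follow-up until after the 1-Year Follow-up", with a carve-out when the 1-year visit was missed and the contact attempts are documented.

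Some year-1 checks are planned. SAP 2.3 has a Kaplan-Meier analysis in the ITT and PP sets, SAP 2.1 makes two-sided 95% intervals the default, and SAP 2.5 promises sensitivity analyses to missing data without naming one.

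**The concern.** A subject with an event counts after any length of follow-up. An event-free subject counts only after the threshold. Three consequences follow.

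- **End date.** If the exit date is one of the collected dates that count, a lost subject last heard from at day 30 normally enters as event-free at 330 days. The rate is then too low even when drop-out has nothing to do with risk.
- **Deaths.** Read literally, a subject who dies before the threshold without the endpoint leaves the denominator, although that subject's status is known.
- **Shrinking denominators.** At years 2-5, events in people who later leave are kept while event-free leavers are removed, so the crude proportion overstates cumulative risk under random drop-out.

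At stake are one pass/fail test with a limit of 23 events in 500, and the long-term rates that will be read as the device's 5-year record.

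**Working it through.** **1. The plan's own figures.** Inputs from SAP 2.3 and 2.4: null 6.9%, target 4.0%, exact test, one-sided 0.025. The limit c(n) is the largest c with P(X ≤ c | n, 0.069) ≤ 0.025.

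- n = 495: c = 23, attained level 2.45%, power P(X ≤ 23 | 495, 0.04) = 80.5%. The stated 495 reproduces.
- 500/0.90 = 555.6, so 556 reproduces.
- n = 500: c = 23 (2.14%). n = 556: c = 26 (1.93%).

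So 24, 25 or 26 events fail on 500 subjects and pass on 556.

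**2. Exit date counted as follow-up, random drop-out.** Assumptions: 556 enrolled; attrition a = 0.10 (SAP 2.4); a share s of TLF on day 1 and the rest uniform to day 365; last contact at day 30, or uniform over days 2-330 (mean 166). The documents give no drop-out timing. The share of a leaver's events that is seen is g = s + (1 − s)t/365.

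All leavers lost and counted: rate = 0.069 × [(1 − a) + a·g]. With s = 0 and t = 30, g = 0.082 and the rate is 0.069 × 0.9082 = 6.27%. Type I error is P(X ≤ 26 | 556, 0.0627) = 6.8%.

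Half lost, half withdrawn and excluded: the excluded fraction is 0.05 × (1 − 0.069 × 0.082) = 0.0497 and the rate is 0.0627/0.9503 = 6.59%. Averaging over the number excluded, type I error is 3.7%.

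| Share of TLF on day 1 | All lost: day 30 / uniform | Half lost: day 30 / uniform |
|---|---|---|
| 0% | 6.8% / 4.2% | 3.7% / 2.2% |
| 25% | 5.0% / 3.5% | 2.7% / 1.8% |
| 50% | 3.7% / 2.9% | 2.0% / 1.5% |

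**3. Follow-up ended at last contact (leavers without an event excluded).** With overall risk F and relative risk r in leavers, the stayers' risk is f = F/[(1 − a) + a·r]. The crude rate is [(1 − a)f + a·r·f·g] / [1 − a(1 − r·f·g)].

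- Random drop-out (r = 1): a true 4.0% appears as 4.0-4.4%. Type I error at 6.9% is 0.4-2.0%, which is conservative.
- r = 2, all leaving at day 30, s = 0: f = 0.069/1.1 = 0.0627; leavers' counted events 0.1255 × 0.082 = 0.0103; rate (0.0565 + 0.0010)/(1 − 0.0990) = 6.4%; type I error 5.4%. With s = 25% it is 3.1%, and with s = 50% it is 1.7%.
- r = 2, uniform departure: 2.1% (s = 0), 1.5% (s = 25%). Departure at day 329, s = 0: 0.6%. All TLF on day 1: 0.5%.

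So at twice the risk the range is 0.5-5.4% for departure at day 30, spread over days 2-330, or later. Universal departure before day 30 would raise the top end somewhat.

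**4. Early deaths dropped, no other loss.** The rate is about F/(1 − D), where D is the proportion dying without the endpoint.

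- 1-year TLF, with D assumed 0.5-2%: 4.0% becomes 4.02-4.08%.
- 5-year TLF, with assumed F = 10.0% and D = 2-7%: 10.2-10.7%.
- A component with a true 5-year rate of 5.0% and D = 5-14%: 5.3-5.8%. The upper D comes from the 14.1% 5-year mortality for Orsiro in BIOSCIENCE (Protocol 15), an all-comers trial.

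**5. Year 5 with random loss.** Constant cause-specific hazards, 5 years taken as 1800 days, threshold 1740 days. Worked case: F = 10%, D = 7%, loss 30%. Over 1800 days the total event-plus-death hazard is −ln(0.83) = 0.1863, split into 0.1096 (TLF) and 0.0767 (death). The loss hazard is −ln(0.70) = 0.3567, so the sum is 0.5430.

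- Still followed at day 1740: exp(−0.5430 × 1740/1800) = 0.5916.
- TLF before day 1740: (0.1096/0.5430) × 0.4084 = 0.0824. TLF from day 1740 to 1800: 0.0021. Deaths without TLF before day 1740: 0.0577.
- Crude rate: 0.0846/(0.0824 + 0.5916) = 12.5%. With those deaths kept in: 0.0846/0.7317 = 11.6%.

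Over 10-30% loss and 2-7% non-cardiac death, a true 10.0% appears as 10.7-12.5%, or 10.4-11.7% if the deaths stay in.

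**6. Tipping point at year 1 (500 evaluable, 56 excluded).** The count that reverses a pass is 26 − x + 1 for x observed events.

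| Observed events | Events among the 56 that reverse the pass |
|---|---|
| 13 (2.6%) | 14 (25.0%) |
| 20 (4.0%) | 7 (12.5%) |
| 22 (4.4%) | 5 (8.9%) |
| 23 (4.6%) | 4 (7.1%) |

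**The case against.** The strongest reply is that nothing in the documents says an administrative exit date is follow-up. SAP 2.3 asks for follow-up data, and Protocol 3.4.4 records the last contact separately. A careful programmer might end follow-up at last contact without being told. That is fair: the inflation in step 2 depends on one reading, and in the half-withdrawn case much of the range lies below 2.5%. But the SAP added the phrase about collected dates and excludes none, so the ambiguity stands.

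A reader might infer that the rule inflates type I error to 5% or more. The documents do not support that. The 5.4% needs doubled risk, every leaver gone by about day 30 and no day-1 events, while TLF includes peri-procedural MI. At twice the risk with departures spread over the year it stays below 2.5%; it takes a larger excess to pass that mark (three times the risk, uniform departure and no day-1 events gives 3.8%).

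A reader might also infer that year 1 has no safeguard. It has the ITT Kaplan-Meier analysis, default 95% intervals and promised sensitivity analyses. What is absent is a named method and a stated comparison with 6.9%. Kaplan-Meier alone would not settle the matter, because it too is biased when loss depends on risk.

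Finally, years 2-5 are descriptive with no hypotheses, and under random loss the bias works against the device. Both points are true, but the reported rate would still be wrong.

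**Conclusion.** The point holds as a gap in specification and a choice of estimator, not as a demonstrated error in the primary test. It should be fixed.

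The firmest parts are the undefined end of follow-up and the crude long-term proportions. Whether exit dates count can decide a result of 24-26 events. The loss of early deaths from the denominator is negligible for 1-year TLF and material by year 5. Informative loss at year 1 is a possibility to be examined, not a shown bias. At an observed 2.6%, as in BIOFLOW-V, 13 of the 56 excluded subjects could have events and the pass would still hold.

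All sizes rest on assumed drop-out timing, event timing and leaver risk. The documents give only 10% attrition in year 1 and no figure for later years; the 5-year TLF, death and loss rates are assumptions.

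Nothing here disputes the sample size. The 495 is correct, and the 79.2% exact power at 500 is ordinary binomial discreteness.

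**What to change.** Keep the exact test as primary. If the 1-year analysis has already been done, label these changes post hoc.

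1. In SAP 2.3 and 2.6, end an event-free subject's follow-up at the last documented contact or the last date with known endpoint status, not at the exit date of a lost subject.
2. Keep subjects who die before the threshold without the endpoint in the denominator as non-events for that endpoint. For TLF these are the non-cardiac deaths.
3. In SAP 2.6, beside the crude proportions at years 2-5, report Kaplan-Meier for all-cause death and cumulative incidence with death as a competing event for the other endpoints, with 95% intervals.
4. Secondary: compare the upper 95% limit of the planned 1-year ITT Kaplan-Meier estimate with 6.9%, and name in SAP 2.5 a tipping-point table that repeats the exact test on all ITT subjects with 0, 1, 2, ... events assigned to those excluded.

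The cost is SAP wording and a few extra outputs. No new data are needed, since the last-contact date is already collected. The downsides are a second figure that may differ from the crude one, and a lower evaluable count if lost subjects would otherwise have been counted by exit date.

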2.4 Sample Size Determination

The estimated sample size for the study is based on TLF results from the BIOFLOW-V study and in consideration of recent published relevant clinical TLF rates of other comparable stents that utilized the SCAI definition² of periprocedural MI. The BIONICS IDE study utilized the Third Universal definition of spontaneous MI⁴, which is deemed to be similar to the spontaneous definition of MI used in the BIOFLOW-V study³.

Comparable stents were evaluated in these two IDE studies involving a total of over 2,000 subjects and had consistent TLF upper 95% confidence bounds in the range of 6.9% - 7.1% (**Table 1**). A performance goal was derived considering this potential TLF rate range and was adjusted to account for the potential differences in the prospectively enrolled BIOFLOW-VII population enrolled under real world post-approval conditions.

Differences in standard of care practices and patient population may impact the final TLF rate. Specifically, cardiac biomarkers are infrequently analyzed post-procedure in asymptomatic patients as standard of care. Analysis of troponins is more frequent in clinical practice, whereas CKMB was measured more frequently as part of the protocol in the BIOFLOW-V study. It is also anticipated that a post-approval real-world population may have different frequencies of factors (e.g. diabetes, prior MI, etc.) and patient and lesion characteristics than those enrolled in IDE trials. These factors could result in a higher observed TLF rate than in BIOFLOW-V or other prior trials.

Study	TLF Rate at 1 Year	95% Confidence Interval
BIOFLOW-V: Orsiro	2.6% (22/833)	(1.7%, 4.0%)
BIOFLOW-V: Xience	4.5% (19/426)	(2.7%, 6.9%)
BIONICS ^{5,6,7} EluNIR	5.4% (50/926)	(4.0%, 7.1%)
BIONICS: Resolute	5.4% (50/930)	(4.0%, 7.0%)

Table 1: 1-Year TLF Rates for DES Utilizing SCAI Definition of Peri-Procedural MI

The sample size required to evaluate the primary endpoint was estimated using the following design criteria:

- Performance goal: 6.9% (upper 95% CI acceptability for BIOFLOW-VII)
- Target Orsiro TLF rate: 4.0%
- Statistical power: 80%
- Significance level: one-sided 0.025

Version 1.0 05-18-2022

Confidential

Do not copy or distribute without sponsor approval

Table 2: Primary Endpoint Sample Size

	Primary Safety Endpoint 1
Sample Size of Evaluable Subjects	495 subjects
Sample Size Adjusted for Post-Approval Study Requirement	500 subjects
Total Adjusted for Attrition	556 subjects

In order to collect additional data on the performance of the Orsiro stent, the sample size was increased to a target minimum of 500 evaluable subjects at 1-year post-index procedure as recommended by the FDA. Assuming a 10% attrition rate through the first 1 year of subject follow-up, a total enrollment of 556 subjects has been estimated.

2.5 Handling of Missing Data in the Analysis of Primary Endpoint

All reasonable methods will be taken to ensure a minimum of missing data. The impact of missing data on conclusions about the primary study endpoint will be examined in sensitivity analyses, which may include multiple imputation methods, if warranted.

2.6 Analysis of Secondary Endpoints

There are no formal hypotheses for the secondary endpoints. The secondary endpoints in the BIOFLOW-VII study will be analyzed using frequentist methods when the time points defined below have been met. For each endpoint, the proportion and denominator will be calculated and reported. Analyses of secondary endpoints will be carried out on the ITT and PP analysis sets when data is available for all subjects at the time point. However, there will be no direct imputation of missing data.

The following secondary clinical endpoints will be evaluated prior to discharge, at 1 month, 1 year and annually thereafter through 5 years of follow-up (refer to Sec. 1.4 for definitions):

- 1) All-cause death
- 2) Protocol-defined MI
- 3) Cardiac death or protocol-defined MI
- 4) MACE and individual MACE components
- 5) TLF and individual TLF components (1-year TLF rate is the primary endpoint)
- 6) TVF and individual TVF components
- 7) Stent thrombosis according to ARC-2 criteria¹

Included in the analysis will be subjects experiencing the event or who have adequate follow-up (e.g., at least 23 days for 1-month time point and at least 330 days for the 1-year time point, 660 days for the 2-year time point, 1020 days for the 3-year time-point, 1380 days for the 4-year time point, and 1740 days for the 5-year time point.)

The following secondary endpoints will also be evaluated (refer to Sec. 1.4 for definitions):

- 8) Device success
- 9) Lesion success

Version 1.0 05-18-2022

Confidential

Page 6 of 11

Do not copy or distribute without sponsor approval

10) Procedure success.

Analysis of secondary endpoints 1-7 will be based on CEC adjudicated event data. Analysis of secondary endpoints 8-10 will be based on site-reported data (with CEC adjudicated event data for endpoint 10, as applicable). In evaluating procedure success, MACE will be based on CEC adjudicated event data.

2.7 Analysis of Baseline Demographics and Procedural Characteristics

Demographic and baseline characteristics, procedural characteristics, lesion characteristics will be reported for the BIOFLOW-VII ITT analysis population. Demographic, medical history and other clinically relevant baseline variables will be summarized using descriptive statistics (i.e. number of observations available, mean, standard deviation, median, first quartile, third quartile, minimum, and maximum for continuous variables and counts and percentages for qualitative variables).

2.8 Comparison with BIOFLOW-V

Patient demographics and target lesion characteristics will be compared with those of the BIOFLOW-V (IDE) Orsiro study cohort to ensure that the enrolled patient population is comparable with the BIOFLOW-V Orsiro (IDE) study population. The analyses at 25%, 50%, and 75% of the expected total enrollment were previously completed and the 100% enrolled population comparison will be performed. Analysis of the target lesion characteristics will be based on site-reported data for both studies since Angiographic Core Lab analysis is not systematically performed for all index procedure angiograms in BIOFLOW-VII.

Treatment difference on dichotomous variables are evaluated using Fisher's exact tests. Categorical variables were compared between studies using the Cochran-Mantel-Haenszel (CMH) Modified Ridit Scores, i.e., CMH of general association for nominal variables and CMH of row mean score for ordinal variables. Continuous variables are compared between studies using two-sample t-tests.

Additionally, comparison between summary 1-year Adverse Event rates may be performed.

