4.3.1 Patient Demographics and Target Lesion Characteristics

Patient demographics and target lesion characteristics will be compared with those of the BIOFLOW-V (IDE) study cohort at 25%, 50%, and 75% of the expected total enrollment to ensure that the enrolled patient population is comparable with the BIOFLOW-V (IDE) study population.

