2.1 Analysis Definitions

Descriptive statistics will be used to present and summarize the data collected in the clinical study. Frequency distributions and cross tabulations will be presented for discrete variables. Means, standard errors, and ranges will be presented for continuous variables. Proportions will be calculated using known non-missing values.

Unless otherwise indicated, all statistical tests and/or confidence intervals will be performed at α = 0.05 (2-sided).

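### SAP 2.8 aims to establish comparability with BIOFLOW-V but names only tests of difference, with no between-study estimate or interval and no stated unit of analysis for lesion variables

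*SAP*

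**What the plan says.** SAP 2.8 gives the purpose of the comparison as "to ensure that the enrolled patient population is comparable with the BIOFLOW-V Orsiro (IDE) study population". Protocol 4.3.1 states the same aim, "to ensure that the enrolled patient population is comparable with the BIOFLOW-V (IDE) study population", and names no method. The SAP narrows the comparator to the Orsiro arm.

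The methods are in the second paragraph of SAP 2.8:

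- Dichotomous variables: "Treatment difference on dichotomous variables are evaluated using" Fisher's exact tests.
- Other categorical variables: "CMH of general association for nominal variables and CMH of row mean score for ordinal variables".
- Continuous variables: "Continuous variables are compared between studies using two-sample t-tests".

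SAP 2.1 sets the default level at two-sided 0.05 for tests and intervals. SAP 2.8 assigns no confidence interval, effect-size measure, margin, decision rule or multiplicity rule to this comparison. SAP 2.7 provides descriptive summaries, but for BIOFLOW-VII alone.

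Target lesion characteristics are among the variables compared, using site-reported data from both studies. Protocol 3.1.5 allows up to three target lesions per subject. SAP 2.8 does not say whether lesion variables are compared per lesion or per subject. The looks at 25%, 50% and 75% of enrolment are complete; the look at 100% is still to be done.

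**The concern.** The aim and the tools do not match. A test of difference can give evidence that two populations differ. Failing to reject does not show that they are alike, because it may only reflect limited power. With many variables tested at 0.05, some will also differ by chance. A column of p-values therefore leaves open how large the differences are.

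That question matters because the study exists to confirm that performance is similar to that in BIOFLOW-V. SAP 2.4 itself expects a real-world population to differ in factors such as diabetes and prior MI, and says this could raise the target lesion failure (TLF) rate. Anyone interpreting the single-arm TLF rate beside the BIOFLOW-V rate will want the size of those differences.

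The lesion variables raise a second issue. The named tests assume independent observations, and lesions within one subject are probably correlated. If the tests are run per lesion, their p-values are too small.

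**Working it through.** **Inputs from the documents.** BIOFLOW-VII size: "a total enrollment of 556 subjects has been estimated" (SAP 2.4). BIOFLOW-V Orsiro cohort: 884 (Protocol Table 1). Level: two-sided 0.05 (SAP 2.1). Maximum of three target lesions per subject (Protocol 3.1.5).

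**Assumed, not in the documents.** Prevalences, true differences, number of variables, lesion-count splits and within-subject correlation (ICC). All 884 and 556 subjects are taken to have data.

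**1. The plan's own figure.** SAP 2.4 inflates 500 evaluable subjects, "Assuming a 10% attrition rate through the first 1 year of subject follow-up": 500 / 0.90 = 555.6, so 556. This reproduces. The documents give no power or margin for the comparison in SAP 2.8, so there is nothing further to reproduce.

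**2. What the tests can see at 100%.** For a standardised difference, SE = √(1/556 + 1/884) = 0.0541.

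- Smallest observed difference that is significant: 1.96 × 0.0541 = 0.106 SD.
- Difference detected with 80% power: 2.80 × 0.0541 = 0.152 SD.
- 40% v 35%: SE = √(0.40×0.60/556 + 0.35×0.65/884) = 0.0262, and power ≈ Φ(0.05/0.0262 − 1.96) ≈ 48%. Simulated power of Fisher's exact test is also about 48%.

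Power of the t-test at each look, from Φ(δ/SE − 1.96):

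| Look | n v 884 | 0.1 SD | 0.2 SD |
|---|---|---|---|
| 25% | 139 | 19% | 59% |
| 50% | 278 | 31% | 83% |
| 75% | 417 | 39% | 92% |
| 100% | 556 | 46% | 96% |

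**3. What an interval would show.** At 100% the 95% interval has half-width 0.106 SD or, for a characteristic near 35%, 1.96 × √(0.35×0.65×(1/556 + 1/884)) = 5.1 points. An observed difference near zero would exclude anything much beyond that.

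**4. Multiplicity.** With 20 independent variables and no true differences, the chance of at least one significant result is 1 − 0.95^20 = 64%.

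**5. Lesion variables, if tested per lesion.** Let m be lesions per subject. Design effect DE = 1 + (E[m²]/E[m] − 1) × ICC, and the true level is 2 × (1 − Φ(1.96/√DE)).

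| Subjects with 1/2/3 lesions | Mean | DE, ICC 0.1 to 0.5 | True level |
|---|---|---|---|
| 83/14/3% | 1.2 | 1.04 to 1.19 | 5.4% to 7.3% |
| 75/20/5% | 1.3 | 1.05 to 1.27 | 5.6% to 8.2% |
| 60/30/10% | 1.5 | 1.08 to 1.40 | 5.9% to 9.8% |

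The only average I found in the documents is 1594/1063 = 1.50 lesions per subject, from the Orsiro arm of BIOSCIENCE, a different, all-comers trial (Protocol 15).

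**6. Would a flag at 0.10 SD do better?** The 40% v 35% example is a standardised difference of 0.05/√((0.24 + 0.2275)/2) = 0.103. The flag fires with probability Φ((0.103 − 0.10)/0.0541) ≈ 52%, against 48% for the test. At zero difference it fires 2 × (1 − Φ(0.10/0.0541)) = 6.5% of the time, against 5.0%.

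**The case against.** The strongest reply is that little depends on SAP 2.8. The primary test uses a fixed goal of 6.9%, and SAP 2.4 says that goal was adjusted for possible population differences. No pass or fail decision rests on the comparison, and nothing says that p-values alone will decide comparability. All of this stands and limits the importance of the point. An indication of scale comes from BIOFLOW-III (Protocol 15), where 1-year TLF was 7.7% with diabetes and 4.0% without. A 5-point imbalance in diabetes alone would then move TLF by about 0.05 × 3.7 = 0.2 points.

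A reader might infer that neither outcome of the tests tells us anything. That goes too far. At full enrolment power is about 96% for 0.2 SD, so a null result is evidence against a large imbalance. A significant result on a subject-level variable is genuine evidence of a difference, apart from multiplicity.

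A reader might also infer that the SAP treats lesions as independent. It does not say so. The unit is unstated, and for reference vessel diameter SAP 2.9 reduces a lesion variable to subject level. The supportable point is that the unit and the handling of correlation are missing. Demographics are unaffected. Multiplicity and ignored clustering both push towards declaring differences, so neither would manufacture a false claim of comparability.

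What remains is the gap between the stated aim and the named methods. Descriptive summaries of BIOFLOW-VII alone do not close it.

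**Conclusion.** The point holds as a mismatch between aim and method. Tests of difference without a between-study estimate and interval cannot establish comparability. At 556 v 884, differences of about 5 points on a 35% characteristic, or 0.1 SD, are missed roughly half the time, while 0.2 SD is rarely missed. The three completed looks had less power.

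For lesion variables the finding is conditional. If they are tested per lesion, the true level is about 5.4% to 8% for mean counts of 1.2 to 1.3 and ICC 0.1 to 0.5, and higher with more lesions per subject. Those counts and correlations are assumptions.

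The effect is on how similarity to BIOFLOW-V is read. The documents do not support extending it to the primary test or its error rate. This is an inexpensive improvement, not a defect in the primary analysis.

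**What to change.** In SAP 2.8, for the 100% comparison:

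- State the unit of analysis for each target lesion variable.
- For every variable report the between-study difference, raw and standardised, with a 95% confidence interval.
- For variables analysed per lesion, use a subject-clustered variance (GEE or robust).
- Base the comparability statement on the size of the differences that the intervals exclude, not on p > 0.05. Do not substitute a flag at 0.10 SD: significance already begins at an observed 0.106 SD, so the flag nearly reproduces the test.

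The p-values may stay for continuity with the 25%, 50% and 75% tables.

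The cost is a little programming and a table format that differs from the completed looks. Protocol 1.3 says patient-level data from prior studies are available, and no new data collection is needed.
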